5.5 Procedures followed and devices used for data collection

A summary of procedures conducted are listed in Appendix B. Phone call interview with collection of PROs was done by one of the research collaborators also in charge of performing the clinical measurements at the center during study visit. The explorations prior to patient recruitment were carried out by an experienced optometrist or physician depending on the required test and the competencies of each professional. For example, the optometrist performed visual acuity and refraction measurements but the physician was responsible of evaluating the PCO, establishing whether the Nd-YAG could lead to improved visual acuity as well as any other tests related to eye health.

5.5.1 Clinical history

- Each patient's medical history was reviewed prior to making the phone call interview.

-
- This first review aims to explore whether the inclusion/exclusion criteria were met before making the call.
 - The variables reviewed in the medical history were:
 - Surgery date
 - Eye and general health
 - Intraocular lens implanted power
 - Adverse events reported in the history during surgery or post-operative follow-up
 - Date of patient's last visit to the clinic
 - Months after surgery on which Nd-YAG capsulotomy was done, if it was the case, and the eye/s

5.5.2 History obtained during the phone call interview

- During the phone call and study visit the patient was consulted about possible diseases and concomitant medications in the 6 months prior to the call or visit.
- The inclusion/exclusion criteria were confirmed through a patient interview for all those issues related to the patient's eye and general health history that might not be found in the medical records.

5.5.3 Patient reported outcomes

- The following questionnaires were carried out during the phone call interview:
 - VF-14 to assess vision-related difficulty in performing everyday tasks.²²
 - PRSIQ to assess independence of spectacles at far, intermediate and near distances.²³
 - Additional questions related to satisfaction, dysphotopsia and decision to have the same MIOL procedure (Appendix C).

5.5.4 Slit-lamp evaluation

The slit lamp examination was performed during the study visit. An examination of the eyelids, conjunctiva, cornea, intraocular lens and anterior vitreous was performed.

- Eye lids: Normal / Non-Normal
- Conjunctive:
 - Hyperemia (Normal / Mild / Moderate / Severe)
 - Oedema (Normal / Mild / Moderate / Severe)
- Cornea: Oedema (Normal / Mild / Moderate / Severe)
- Staining: Anterior chamber cells and flare.²⁴
- Anterior Capsular Opacification:²⁵ From 0 to 4 grading
- Posterior Capsular Opacification (PCO):²⁶ From 0 to 4 grading density
- Intraocular lens centration: ²⁷ From 0 to 4 grading
- Vitreous:²⁸ From 0 to 4 grading
- IOL calcification:²⁹ (None / primary / secondary)

5.5.5 Pentacam AXL

A measurement was performed with Pentacam AXL (corneal tomograph with Scheimpflug technology and ocular biometer, Oculus, Germany) to evaluate that the patient met the inclusion criteria in reference to irregular corneal astigmatism and to collect the necessary ocular demographic data for the results report. The following variables were collected with the Pentacam AXL:

- Irregular astigmatism at 4 mm (μm): For Total Cornea (anterior and posterior corneal surfaces combination).
- Anterior lens position (mm): Distance from anterior corneal vertex to anterior intraocular lens.
- Regular astigmatism (D): For Total Cornea.

- Corneal spherical aberration for mesopic pupil size (μm): Recalculated for the mesopic pupil diameter and the Total Cornea.

5.5.6 IOL Master 500

A measurement was performed with IOL Master 500 to obtain:

- Axial length (mm)
- Mean corneal anterior keratometry (D). Average from the steep and flat axis measured for the anterior cornea.

5.5.7 Keratograph 5M

A measurement was carried out for collecting the following variables:

- Photopic pupil diameter (mm)
- Mesopic pupil diameter (mm)

5.5.8 Subjective Refraction

Subjective refraction was performed with a trial frame following our specific protocol for MIOs.

- The optotype used to carry out the refraction (ETDRS) was placed at a distance of 4 m with a background luminance of 85 cd/m² (VisionC ETDRS chart, test-eye.com).
- Based on the patient's spectacle refraction (if used), the objective refraction with auto-refractometer, and the corneal astigmatism obtained with Pentacam, the starting sphere and cylinder were selected.
- A 1.00 D myopization with positive spherical lenses was performed in order to shift the defocus curve enough to avoid refraction at a distance over the near focus.
- After reaching the maximum positive maximum visual acuity (MPMVA), patient was myopized with +0.50 D and the axis and magnitude of the cylinder was fitted with a cross cylinder of +/- 0.50 D.

- The procedure was completed by returning to the MPMVA and adding -0.25D on the sphere to obtain the equivalent refraction in infinity considering the proximal distance induced myopia ($1/-0.25 = 4\text{m}$).
- The procedure was completed with a confirmation of +/- 2.50 D so that the negative lens slightly decreases visual acuity (2 lines) and the positive lens significantly decreases visual acuity. This procedure served as confirmation that the refraction was carried out at the focus corresponding to distant vision.

5.5.9 Visual acuity

- Measured in monocular vision with and without the best correction obtained in the subjective refraction.
- Measured in binocular vision without correction.
- Measurements conducted at three distances:
 - Infinity: 4 m with distance vergence correction (+0.25 D)
 - Intermediate: 67 cm
 - Near: 40 cm
- The procedure for measuring visual acuity was carried out with the ETDRS optotype chart (VisionC ETDRS chart, test-eye.com), selecting different sets of letters for each eye and distance in order to avoid a possible bias due to the effect of memorizing letters.
- The procedure for determining the visual acuity threshold was carried out as follows:
 - Read only the first letter from the left and go down.
 - At the first failure, stayed on the previous line and read the whole line.
 - If correct answers were $\geq 3/5$ advanced to the next line.
 - If correct answers were $< 3/5$ read the previous line.
 - Visual acuity was the last with correct answers $\geq 3/5$.

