5.6.1 Hypothesis and sample size calculation

5.6.1.1 Main hypothesis (non-inferiority)

The primary objective was to assess long-term efficacy by measuring monocular visual acuity with and without correction at distance (CDVA and UDVA), intermediate (DCIVA and UIVA) and near (DCNVA and UNVA). The mean monocular visual acuity and the standard deviations taken as reference were obtained from previous literature.¹⁵ Visual acuity was measured on a logMAR scale so that the smaller the variable, the higher the visual acuity.

A contrast of non-inferiority hypotheses with unilateral significance was carried out, rejection of null hypothesis means that non-inferiority was accomplished:

$$H_0 = \mu_a \geq \delta + \mu_b$$

$$H_A = \mu_a < \delta + \mu_b$$

H_0 = Visual acuity at 6 years was higher or equal (poorer) than at 12 months plus a margin δ

H_A = Visual acuity at 6 years was lower (better) than at 12 months plus a margin δ

μ_a = Mean monocular visual acuity obtained after 6 years of follow-up

μ_b = Mean monocular visual acuity reported in a previous clinical study with 12 months of follow-up.¹⁵

δ = 0.1 logMAR or 0.02 logMAR

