5.6.1.2 Study power

The statistical test planned in the protocol for testing the hypothesis was the one-sided one-sample t-test but the one-sided one-sample Wilcoxon Signed test was finally used due to non-normal distribution of the variables. The margin (δ) selected in the protocol was 0.1 logMAR but the hypothesis was finally also confirmed with a margin of 0.02 logMAR. The software G-Power 3.9.1.2 (Universität Düsseldorf) for an alpha level of 0.05 was used to calculate the power considering the standard deviation obtained in our study.

Table 1. Sample size confirmation

Variables	μ_a	μ_b	Power $\delta = 0.1$	Power $\delta = 0.02$
UDVA	0.06 ± 0.12 0.1 [0.1]	0.03 ± 0.13 0 [-]	0.96	0.12
CDVA	-0.05 ± 0.07 -0.1 [0.1]	0.01 ± 0.11 0 [-]	1	0.99
UIVA	0.07 ± 0.09 0.0 [0.1]	0.12 ± 0.13 0.1 [-]	1	0.99
DCIVA	0.08 ± 0.09 0.1 [0.1]	0.11 ± 0.12 0.1 [-]	1	0.94
UNVA	0.08 ± 0.10 0.1 [0.1]	0.27 ± 0.15 0.2 [-]	1	1
DCNVA	0.05 ± 0.06 0 [0.1]	0.25 ± 0.14 0.2 [-]	1	1

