5.6.2 Statistical analysis methods

- Normal distributions were tested with the Shapiro-Wilk test
- Wilcoxon-signed rank test one sample was finally selected for testing the hypothesis for median differences because of the non-normal distribution of the variables.
- Correlations were assessed with the Spearman rho or Multiple Linear Regression for multiple correlations and a single dependent variable.
- Descriptive statistics are detailed in the results section as mean ± standard deviation [median (interquartile-range)].
- A survival analysis was performed for the assessment of Nd:YAG rates.
- SPSS version 24 software (SPSS Inc, Chicago, IL, USA) was used for the statistical analysis.

- The Refractive Analysis toolbox for MATLAB (R2019; MathWorks, Natick, MA, USA) was used for conducting the standard plots.³⁰

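### Acuity is scored by whole lines of 0.1 logMAR, which discards letter information and distorts the one-sample Wilcoxon test used for non-inferiority, while costing a mean-based analysis little

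*Combined protocol and SAP*

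**What the plan says.** Section 5.5.9 states: "The procedure for measuring visual acuity was carried out with the ETDRS optotype chart". The patient reads first letters down the chart until the first failure, goes back one line, and then reads whole lines. Three or more of five correct leads to the next line; fewer leads back to the previous one. The recorded value is the line itself: "Visual acuity was the last with correct answers" on at least 3/5. No credit for single letters is described.

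Section 5.6.1.1 sets the scale, "Visual acuity was measured on a logMAR scale so that the smaller the variable, the higher the visual acuity", and gives the margin as "δ = 0.1 logMAR or 0.02 logMAR". Section 5.6.1.2 explains the two values: "The margin (δ) selected in the protocol was 0.1 logMAR but the hypothesis was finally also confirmed with a margin of 0.02 logMAR". The planned one-sample t-test was replaced: the "one-sided one-sample Wilcoxon Signed test was finally used due to non-normal distribution of the variables". Section 5.6.2 repeats this: "Wilcoxon-signed rank test one sample was finally selected for testing the hypothesis for median differences".

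In Table 1 all six 6-year medians and interquartile ranges are multiples of 0.1.

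**The concern.** The unit of recording is as large as the planned margin and five times the added one. With five letters to a 0.1 line, the 0.02 margin is one letter. The scoring rule ignores up to two letters missed on the credited line and up to two read on the next line, so one eye's score can differ from its letter score by 0.04 in either direction. All six primary endpoints carry this rounding.

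The coarse scale also bears on the choice of test. Values on a few grid points produce ties and can fail a normality test for that reason alone, and non-normality is the stated reason for moving to Wilcoxon. A signed-rank test is sensitive to where its test value falls between grid points. The error rate of the primary comparison is therefore at stake, at the planned margin as well as at the small one.

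**Working it through.** **Inputs.** Table 1 gives 6-year mean ± SD and reference mean: UDVA 0.06 ± 0.12 against 0.03; CDVA -0.05 ± 0.07 against 0.01; UIVA 0.07 ± 0.09 against 0.12; DCIVA 0.08 ± 0.09 against 0.11; UNVA 0.08 ± 0.10 against 0.27; DCNVA 0.05 ± 0.06 against 0.25. The synopsis gives n=37, and section 5.6.1.2 gives one-sided alpha 0.05. The 0.1 step is inferred from the chart type.

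**Reproducing Table 1.** One-sided power from the noncentral t, with d = (μb + δ − μa)/SD and n multiplied by 3/π for Wilcoxon, matches all 12 cells within 2 points. For example, UDVA at δ=0.1 is 0.960 (stated 0.96) and DCIVA at δ=0.02 is 0.944 (stated 0.94). UDVA at δ=0.02 gives the stated 0.12 only if the sign of the effect is ignored. The signed t-test value is 0.016.

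**Step against margin.** 0.1/0.1 = 1; 0.1/0.02 = 5; one letter = 0.1/5 = 0.02.

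**Error in one eye.** Line score minus letter score, for 0 to 4 letters read on the next line: 0, +0.02, +0.04, −0.04, −0.02. The mean is zero if these counts are equally likely.

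**Cost for a mean.**
- Rounding variance is 0.1²/12 = 0.000833 (SD 0.029) for lines and 0.02²/12 = 0.000033 (SD 0.006) for letters.
- The line value is 0.000833/0.0144 = 5.8% of the UDVA variance and 0.000833/0.0036 = 23.1% of the DCNVA variance.
- The avoidable part is 0.0008, or 5.6% to 22.2%. The cut in standard error is 1 − √(1 − 0.056) = 2.8% to 1 − √(1 − 0.222) = 11.8%.
- t-test power moves from 0.967 to 0.974 (UDVA, δ=0.1) and from 0.953 to 0.968 (DCIVA, δ=0.02). Other cells barely change.
- One-sided 95% upper bounds for the mean difference, line then letter: UDVA 0.063, 0.062; CDVA −0.041, −0.042; UIVA −0.025, −0.026; DCIVA −0.005, −0.006; UNVA −0.162, −0.163; DCNVA −0.183, −0.185. None crosses a margin.

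**Cost for Wilcoxon.** Wherever the test value lies between two adjacent grid points, each eye keeps the same sign. Against the UDVA reference median of 0, margins of 0.02 and 0.08 sort the eyes identically into better and worse; only the ranks can differ. The ranks can also tilt. For CDVA at δ=0.1 the test value is 0.01 + 0.1 = 0.11. An eye at 0.0 is 0.11 better and an eye at 0.2 is 0.09 worse, so the better eye always outranks the worse one. For UNVA at δ=0.02 the value is 0.29: an eye at 0.2 is 0.09 better and an eye at 0.4 is 0.11 worse, so the tilt reverses.

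Simulated Wilcoxon type I error at the margin follows (nominal 0.05; 5,000 trials per cell, n=37, normal latent acuity rounded to 0.1 or 0.02, test value μb+δ, zeros dropped, ties corrected):

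| Endpoint | δ=0.1 line | δ=0.1 letter | δ=0.02 line | δ=0.02 letter |
|---|---|---|---|---|
| UDVA | 0.039 | 0.052 | 0.043 | 0.045 |
| CDVA | 0.436 | 0.049 | 0.038 | 0.057 |
| UIVA | 0.122 | 0.053 | 0.006 | 0.048 |
| DCIVA | 0.292 | 0.052 | 0.034 | 0.048 |
| UNVA | 0.089 | 0.047 | 0.008 | 0.055 |
| DCNVA | 0.047 | 0.045 | 0.103 | 0.051 |

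The t-test stays between 0.043 and 0.057 under either scoring. In a separate simulation on the same model, rounding to 0.1 alone made Shapiro-Wilk reject normality in 94% to 100% of samples.

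**The case against.** The strongest reply is that a margin applies to a group, not to an eye. The mean of 37 eyes moves in steps of 0.1/37 = 0.0027, and rounding contributes only 0.029/√37 = 0.005 to its standard error, about a quarter of a letter. A reader might infer that a 0.1 scale cannot register a 0.02 margin at all. For means that is wrong, and setting a per-eye error of 0.04 against a group margin of 0.02 compares unlike quantities. This part of the reply stands in full.

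It can also be said that the fault lies in the test rather than the chart, since the planned t-test holds its level with line scores. That is true, and it supplies a remedy that needs no rescoring. But Wilcoxon holds its level with letter scores too, so it is the combination that fails, and the combination is what was used.

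Two points on evidence also stand. Medians printed to one decimal would look the same whatever the scoring, so Table 1 is consistent with a 0.1 grid but does not prove it. And counting to 3/5 does not show that the counts were written down.

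Finally, the documents do not say whether the Wilcoxon test value was the reference mean or the reference median plus δ. With the medians (0, 0.1 or 0.2), δ=0.1 puts the test value on a grid point, and the tilt at that margin disappears. At δ=0.02 it does not: against 0.12, an eye at 0.0 is 0.12 better and an eye at 0.2 only 0.08 worse.

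**Conclusion.** The point holds as a worthwhile improvement, not as a fault that overturns results. Whole-line scoring discards letters that the procedure already has the patient read. For means the loss is a standard error that letter scoring would cut by 2.8% to 11.8%, with no conclusion changed. For the Wilcoxon test used, error control on a 0.1 grid is unreliable: about 0.01 to 0.43 in place of 0.05. Those sizes are illustrative and rest on a 0.1 step, normal latent acuity, n=37 and a test value of μb+δ. They describe behaviour at the margin, and most Table 1 effects lie well inside it.

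A reader might infer that line scoring invalidates the non-inferiority findings, or that it explains any failure at 0.02. Neither is supported. On means, five endpoints clear 0.02 with line scores. UDVA does not, under either scoring: its mean of 0.06 exceeds 0.03 + 0.02 = 0.05, and the upper bound for its difference is 0.03 + 1.688 × 0.12/√37 = 0.063. The statement that the hypothesis was also confirmed at 0.02 therefore fails for UDVA on its mean, for a reason separate from scoring.

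**What to change.** 1. If per-line letter counts were kept, rescore from the source sheets: the value of the credited line, plus 0.02 for each letter missed on it, minus 0.02 for each letter read on the next line, with larger lines assumed read. Use this value in the primary analysis.
2. If they were not kept, state line scoring as a limitation. Base non-inferiority on the mean difference with a one-sided 95% bound rather than on the Wilcoxon test, and do not rest the 0.02 claim on the Wilcoxon result.
3. Either way, state how the 12-month reference study scored acuity. The documents do not say, and if it used lines, rescoring only this cohort would create a mismatch that matters at a one-letter margin. Reporting both scorings would show its size.
4. State the exact Wilcoxon test value for each endpoint, and correct the 0.02 statement for UDVA.

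The cost is rescoring work on visits completed in November 2020 or, in a future study, slightly more recording. The procedure already ends with both the threshold line and the next line read, except at the end of the chart, so little extra testing is needed. The fallback in step 2 needs no new data.

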5.5.10 Contrast sensitivity defocus curve

- The Multifocal Lens Analyzer App (defocuscurve.com) was used to evaluate the Contrast Sensitivity Defocus Curve in monocular vision (one eye selected at random).
- Patient sitting 4 m from the iPad with +0.25 D vergence correction lens on trial frame over the best correction at infinity.
- The automated procedure varies the contrast for a 0.3 logMAR Snellen optotype equivalent size in steps of 0.1 logCS and uses a staircase psychophysical method to determine the contrast sensitivity threshold.
- The procedure is repeated for each defocus lens until a range of 11 lenses is completed from +1.00 D to -4.00 D in steps of -0.50 D.
- Areas Under the Curve (AUCs) were computed along the total range (Total Area Under the Curve (TAUC), +1.00 to -4.00 D) and for the ranges of Far (Far Area Under the Curve (FAUC), +0.50 to -0.50 D), (Intermediate Area Under the Curve (IAUC), -0.50 to -2.00 D) and Near vision (Near Area Under the Curve (NAUC), -2.00 to -4.00 D).

5.5.11 Light Distortion Analyzer

- Measurement with the Light Distortion Analyzer (CEORLab, University of Minho, Braga, Portugal) were performed under monocular conditions (one eye randomly selected) with the subjective refraction at distance and uncorrected binocular vision or with the usual correction used by the patient.
- The Light Distortion Analyzer was used to psychophysically measure the light effects perceived by the patient around light sources such as car headlights, streetlights, etc.
- The test consists of a central LED and peripheral LEDs with a luminance ratio of 100/1 so that the central LED generates the light distortion and the peripheral LEDs are activated in an automated way by scanning the visual field through the random inspection of each semi-meridian and 3 repeated measurements in each semi-meridian.
- The scanning protocol is called "in-out 30°" in which the peripheral points around the central source are presented from the inside to the outside of the evaluated field in random

time intervals between 500 and 750 milliseconds. The peripheral LEDs turn on and off sequentially in the same semimeridian from the center to the periphery, the scanning of the different semimeridians were randomized by the device.

- The measurement was carried out at 2 m with +0.50 D to correct the vergence produced by the presentation distance with the lighting of the room in mesopic conditions.

[figure not shown]

Figure 2. Example of a measurement with the Light Distortion Analyzer.

Figure 2 shows an example of the field explored described by three main variables:

- BFC Irregularity (mm): Average distance from disturbance to Best Fit Circle (BFC) along each semi meridian.
- BFC Radius (mm): radius of the circle that best fits the distortion area.
- Disturbance Index (%): percentage of the area over the Total Tested Area.

5.6 Statistical analysis plan

- Statistical analysis was performed with SPSS 24

- Standardized descriptive graphics were represented with the Refractive Analysis Toolbox library (version 1.0.5) for MATLAB (<https://www.test-eye.com/en/refractive-analysis>)

5.6.1 Hypothesis and sample size calculation

5.6.1.1 Main hypothesis (non-inferiority)

The primary objective was to assess long-term efficacy by measuring monocular visual acuity with and without correction at distance (CDVA and UDVA), intermediate (DCIVA and UIVA) and near (DCNVA and UNVA). The mean monocular visual acuity and the standard deviations taken as reference were obtained from previous literature.¹⁵ Visual acuity was measured on a logMAR scale so that the smaller the variable, the higher the visual acuity.

A contrast of non-inferiority hypotheses with unilateral significance was carried out, rejection of null hypothesis means that non-inferiority was accomplished:

$$H_0 = \mu_a \geq \delta + \mu_b$$

$$H_A = \mu_a < \delta + \mu_b$$

H_0 = Visual acuity at 6 years was higher or equal (poorer) than at 12 months plus a margin δ

H_A = Visual acuity at 6 years was lower (better) than at 12 months plus a margin δ

μ_a = Mean monocular visual acuity obtained after 6 years of follow-up

μ_b = Mean monocular visual acuity reported in a previous clinical study with 12 months of follow-up.¹⁵

δ = 0.1 logMAR or 0.02 logMAR

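### Non-inferiority rests on rejecting H0 alone, with no estimate or confidence limit for the 6-year minus 12-month difference; this hides that UDVA does not support the 0.02 logMAR claim on the mean scale

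*Combined protocol and SAP*

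**What the plan says.** Section 5.6.1.1 compares the mean acuity at 6 years (μ_a) with a mean published for 12 months (μ_b). It does so for UDVA, CDVA, UIVA, DCIVA, UNVA and DCNVA, on the logMAR scale where higher is worse. "A contrast of non-inferiority hypotheses with unilateral significance was carried out", and "rejection of null hypothesis means that non-inferiority was accomplished". The hypotheses are written on means, with the margin given as "δ = 0.1 logMAR or 0.02 logMAR".

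Section 5.6.1.2 explains the two margins: "The margin (δ) selected in the protocol was 0.1 logMAR but the hypothesis was finally also confirmed with a margin of 0.02 logMAR". The planned test was a one-sided one-sample t-test, but "the one-sided one-sample Wilcoxon Signed test was finally used due to non-normal distribution of the variables". Section 5.6.2 describes that test as one of median differences. On power, 5.6.1.2 says "The software G-Power 3.9.1.2 (Universität Düsseldorf) for an alpha level of 0.05 was used to calculate the power", using the SD observed in this study.

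Table 1 gives, for each acuity, the 6-year and reference summaries and a power value for each margin. Section 5.6.2 otherwise plans means, SDs, medians and interquartile ranges. Neither these sections nor the synopsis plans an interval or limit for the difference.

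**The concern.** A test at a fixed margin returns pass or fail. Two acuities can both pass at 0.1 logMAR when one is better than its reference and the other is worse by a good part of the margin. A 6-year efficacy claim needs the estimated change and the largest loss the data still allow.

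The power columns do not supply this. They are computed after the fact from the observed SD, and they describe the chance of rejection under an assumed effect, not the size of the effect.

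The omission matters most at the second margin. Section 5.6.1.2 says the hypothesis was also confirmed at 0.02 and names no exception. If any acuity lies beyond 0.02, a difference with its upper limit would show it at once. A power value would not.

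**Working it through.** **Inputs.** Table 1 gives the means and SDs. The synopsis gives n = 37 for visual performance. Section 5.6.1.2 gives alpha 0.05, applied one-sided as in 5.6.1.1. The reference mean is held fixed, as the plan does.

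**Step 1: reproduce Table 1.** Effect size = (μ_b + δ − μ_a)/SD, with one-sample one-sided noncentral-t power and n multiplied by 3/π for the Wilcoxon test.
- UDVA, δ = 0.1: (0.03 + 0.10 − 0.06)/0.12 = 0.583, power 0.960 (printed 0.96).
- DCIVA, δ = 0.02: (0.11 + 0.02 − 0.08)/0.09 = 0.556, power 0.944 (printed 0.94).
- UDVA, δ = 0.02: (0.03 + 0.02 − 0.06)/0.12 = −0.083. The printed 0.12 is reproduced (0.123) only if the minus sign is dropped. With the sign kept, power is about 0.016.

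With that exception, all 12 values agree within two percentage points at n = 37. At n = 74 eyes they do not (UDVA at δ = 0.1 would be 0.999), so 37 is the right n for Table 1.

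**Step 2: the missing limit.** One-sided 95% upper limit = (μ_a − μ_b) + t(0.95, 36) × SD/√37, with t = 1.688 and √37 = 6.083. For UDVA: 0.06 − 0.03 + 1.688 × 0.12/6.083 = 0.030 + 0.033 = 0.063.

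| Acuity | μ_a − μ_b | Upper limit | Below 0.1 | Below 0.02 |
|---|---|---|---|---|
| UDVA | +0.03 | +0.063 | yes | no |
| CDVA | −0.06 | −0.041 | yes | yes |
| UIVA | −0.05 | −0.025 | yes | yes |
| DCIVA | −0.03 | −0.005 | yes | yes |
| UNVA | −0.19 | −0.162 | yes | yes |
| DCNVA | −0.20 | −0.183 | yes | yes |

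**Step 3: UDVA at 0.02.** t = (0.06 − 0.05)/(0.12/6.083) = 0.01/0.0197 = 0.51 on the null side, so the one-sided p for non-inferiority is 0.69. The estimated difference of 0.03 itself exceeds 0.02, so with that mean no sample size brings the limit below 0.02.

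**Step 4: rounding.** Moving both means and the SD by ±0.005 gives a UDVA limit of 0.052 to 0.075 and p at 0.02 of 0.50 to 0.85. DCIVA runs from −0.016 to +0.006. No reading in the table changes.

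**Step 5: reference not fixed.** The reference sample size is not in the documents, so 30, 60 and 120 are assumptions. Limit = 0.03 + 1.645 × √(0.12²/37 + 0.13²/N) = 0.081, 0.073 and 0.068. UDVA still lies between 0.02 and 0.1. DCIVA at N = 30 moves to about +0.014.

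**The case against.** A reader might infer that the plan never says how much loss it excludes. The documents do not support that. Rejecting H0 at δ with one-sided alpha 0.05 excludes a loss of δ. For the planned t-test it is the same as a one-sided 95% upper limit below δ. The plan names that loss as 0.1, and also claims 0.02. What is missing is the distance of each acuity from the margin.

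It can also be said that Table 1 prints both means and the SD, so the limits can be derived without testing another margin, and that descriptive results are deferred to a results section not among these documents. Both are true, and what was finally reported cannot be judged. But the reader should not have to derive the primary estimate, and the power columns point away from the UDVA problem.

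The strongest objection is that the test used was the Wilcoxon, so a t-based limit answers a different question and could disagree with it. This stands in part. The Wilcoxon result cannot be rerun without patient data, so the arithmetic does not prove that the test failed to reject at 0.02. The t-based limit still fits H0 as written on means, and the t-test was the planned test. The matching Hodges-Lehmann limit should be shown as well.

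A fixed reference also makes every limit optimistic, as step 5 shows.

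**Conclusion.** The point holds in this form. Non-inferiority is decided by rejection alone, only observed-SD power stands beside each margin, and no difference or limit is planned. All six acuities meet the protocol margin of 0.1 on the mean scale, with upper limits from −0.183 to +0.063 logMAR. For UDVA the data still allow a loss of more than half of the 0.1 margin, and the unqualified confirmation at 0.02 is not supported on the mean scale.

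This rests on the printed means and SDs, n = 37, a t-based limit and a fixed reference. The UDVA reading survives rounding and the assumed reference sizes of 30 to 120.

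A reader might go further and infer that UDVA fails at 0.1, because the printed medians are 0.1 and 0. That does not follow. The medians are printed to one decimal, the signed-rank test does not compare sample medians directly, and the mean-based limit is below 0.1 throughout.

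**What to change.** In 5.6.1.1, state that for each acuity the estimate of μ_a − μ_b and its one-sided 95% upper limit will be reported, and that non-inferiority is judged against the pre-specified 0.1 logMAR. Use the t-based limit for the mean, and say openly that this follows the hypotheses as written and the planned test. Beside it give a bootstrap limit, and a Hodges-Lehmann estimate and limit that match the Wilcoxon test. Where they disagree, report both.

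In Table 1, show the difference and its upper limit in place of the power columns or beside them. If the power columns stay, correct the UDVA entry at 0.02 for the sign of the effect.

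In 5.6.1.2, label 0.02 as post hoc and state that UDVA does not meet it on the mean scale.

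Add a sensitivity limit that allows for error in the reference mean, using the sample size of the cited 12-month study.

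The cost is wording, one table and a small amount of analysis on data already held. The conclusion at 0.1 on the mean scale is kept, and the UDVA statement becomes less favourable.
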